All allowed concomitant medications will be unchanged throughout the study. Other psychotropic medications will require a 2-4 week washout, depending on the half life of the applicable medication after the subject is deemed eligible after the screening visit. Subjects will be monitored weekly by phone for side effects or symptom worsening during the taper. Subjects randomized to the Levomilnacipran switch arm will have their SSRI tapered over 2-4 weeks after they are determined to be eligible for the study to avoid risk of discontinuation syndrome. Subjects randomized to the adjunctive quetiapine arm will have their pre-existing antidepressants continue unchanged at baseline. A flexible dose regime of levomilnacipran ER 40-120 mg/d mg per day will be followed with the FDA approved package insert. Initial titration dose will be 20 mg/d Days 1-2, increasing to 40 mg/d from Days 3-7 in week 1, flexibly dosed between 40 mg/d - 120 mg/d week 2 to week 8. FDA approved package insert guidelines will be followed for adjunctive quetiapine dosing. Adjunctive quetiapine will be started at 50 mg/d Day 1-2, increasing to 150 mg/d Days 3-7 and flexibly dosed between 150-300 mg/d week 1-8. Patients who cannot tolerate the higher dose of levomilnacipran ER or quetiapine will have their dose reduced to the lower dose per the investigator's judgment. At the end of the 8-week trial, subjects in each group will have 1-week taper of study drug. A week 9 follow up safety assessment will be performed. Subjects will be told how to safely restart their

prior medication or can be provided with a referral for continued treatment as needed.

Any new medication started during the study will be evaluated by the investigator to determine its effect on study integrity and subject safety. Subjects and primary raters will be blinded to study drug and doses.

Arm I: Levomilnacipran ER flexible dose regime (40-120 mg/d): titration dose of 20 mg po once a day from days 1-2, then 40 mg po once a day, 80mg po once a day or 120 mg once a day.

Arm II: Quetiapine flexible dose regime: 50 mg po once a day as initiating dose, 150 mg po once a day (during the period that the subjects will be titrated on 150 mg; they will be given 1-50mg tab and 1-100 mg tab with instructions to be taking once per day) (, then 300 mg po once a day.

C. Visit specific procedures and sequence:

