Using Cohen's d effect size to determine sample size, in Cohen's standard text on statistical power (Cohen, 1988), using the NICE definition of a $d=0.5$ or larger, we obtain an estimated sample size (given a two-sided $\alpha = 0.05$ and $1 - \text{Beta} = 0.800$) of $n= 30$ per arm or 60 for the study. A power analysis was also conducted based on an effect size estimate derived from the drug-placebo difference in primary outcome of MADRS scores in published levomilnacipran trials (Citrome, 2013). The summary of Least square mean change between drug and placebo at 95% CI was -4.9 ($p<.0001$). With a two-tailed $\alpha= 0.05$, a sample size of $n= 60$ provides a power of 0.80.

B. Randomization Method

Randomization will occur with randomly generated computer lists held at the Duke site. This group will assign subjects according to a computer-generated the randomization sequence (without blocking or stratification) for each site. After the study coordinator determines eligibility, the participant will be randomized to one of two different arms. Drug capsules will be placed in standard medicine bottles. Each bottle will be dispensed individually by the study coordinator at the appropriate visit. Rater unblinding will be done at the end of the study after data lock. In case of any AEs or SAEs or other emergencies that require the blind to be broken, the pharmacy will have a 24-hour on call support service.

Power analysis was performed using an internet based software program. The results showed that a sample size of $n=60$ ($n=20$ in each of the 3 groups) could detect a strong effect with $\alpha = .05$, unless the true mean difference is quite minimal.

C. Plan of Data analysis

Subjects will be defined as able to be evaluated by two methods. The primary method will be an intent-to-treat analysis, including those who discontinue drug due to lack of efficacy or due to side effects. The secondary method will be completer analysis. The intent-to-treat (ITT) group will include randomly assigned patients receiving study drug with a post baseline efficacy assessment. The safety population will comprise all patients receiving study drug with a post baseline safety assessment.

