Primary efficacy analysis will be conducted in the ITT population using the last-observation-carried-forward (LOCF) method. Treatment group comparisons will base on changes in MADRS from baseline to week 8/end of treatment from repeated measures ANOVA or analysis-of-covariance (ANCOVA) model containing treatment site, gender and baseline MADRS score included as a covariate.

Secondary efficacy analysis: Repeated measures ANOVA or ANCOVA models will be used to analyze change from baseline in secondary measures. Response and remission rates at end of treatment will be compared using the Cochran-Mantel- Haenszel test. No formal hypothesis testing will be performed on safety data. Safety outcomes will be summarized by treatment group and study visit (observed cases) using descriptive statistics. Any clinically significant findings among patients who terminated early will be discussed separately. All analyses will be conducted using SAS Version 9.1.3 (SAS Institute, Inc.; Cary, North Carolina). Statistical comparisons of efficacy outcomes will be 2-sided and considered significant at $P < .05$. Comparisons for secondary endpoints will be not adjusted for multiplicity.

D. Definition of Evaluable Subject (Safety and Efficacy)

Subjects will be defined as able to be evaluated by two methods. The primary method will be an intent-to-treat analysis, including those who discontinue drug due to lack of efficacy or due to side effects. The secondary method will be completer analysis.

XI: ETHICAL AND REGULATORY CONSIDERATIONS

A. Institutional Committee Approval

Duke University Health Systems Institutional Review Board (DUHS IRB) will need to approve the protocol at the Duke site. [name] site will use an external IRB (e.g. Copernicus, Western) and provide Duke with a copy of its approval.

B. Informed Consent

Participation in this study is voluntary and at no cost to the subjects. All potential participants interested in this study must be thoroughly informed of the details of the study. Prior to study participation in this trial, each subject will have an opportunity to ask questions and will sign an approved informed consent form. The signed consent forms will be filed with the investigator's copies of the Case Report Forms for each subject and a copy provided to the subject. Any subject may voluntarily withdraw from the study at any time without prejudicing treatment.

C. Document Storage and Retention

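### The primary set is labelled intent-to-treat but is a modified ITT set: randomised patients with no dose or no post-baseline rating are dropped, and an SSRI taper confined to the switch arm could make those losses unequal

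*Combined protocol and SAP*

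**What the plan says.** Section VII.C of the statistical evaluation defines the intent-to-treat group as "randomly assigned patients receiving study drug with a post baseline efficacy assessment". It then states: "Primary efficacy analysis will be conducted in the ITT population using the last-observation-carried-forward (LOCF) method". The intent-to-treat method is described as "including those who discontinue drug due to lack of efficacy or due to side effects", which covers patients who started drug and stopped. It does not mention patients who never started or were never rated. The alternative is narrower: "The secondary method will be completer analysis". Section VII.D repeats these two methods and adds no other. The safety population also requires study drug and a post-baseline assessment.

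On the period before treatment, section V.B says: "Subjects randomized to the Levomilnacipran switch arm will have their SSRI tapered over 2-4 weeks after they are determined to be eligible". For the other arm it says: "Subjects randomized to the adjunctive quetiapine arm will have their pre-existing antidepressants continue unchanged at baseline". During the taper the plan provides telephone contact: "Subjects will be monitored weekly by phone for side effects or symptom worsening during the taper". No MADRS is stated for those calls.

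On timing, section VII.B randomises a participant once the coordinator has determined eligibility. The schedule of events (XIV) places randomisation at the Week 0 baseline visit, and section V.C lists dispensing of study drug at that visit.

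**The concern.** The primary objective compares two strategies, switching and augmentation, on efficacy and tolerability. Stopping the SSRI is part of switching. If a patient is assigned to switch, worsens or leaves while the SSRI is withdrawn, and never takes levomilnacipran, the written definition removes that patient from the primary analysis, the completer analysis and the safety population. The patient then counts against the strategy nowhere.

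Randomisation protects the comparison only while membership of the analysis set does not depend on what happens afterwards. Here it does, and one arm may have an extra step at which patients can be lost. Treatment is not concealed from those managing it in the way a double-blind trial would ensure (the protocol describes the trial as rater-blinded), so early departures related to the assigned strategy are plausible. With 30 patients per arm, each excluded patient is 1/30 = 3.3% of an arm.

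**Working it through.** The plan gives no dropout rate, no MADRS standard deviation and no figure for exclusions, so there is no plan figure to reproduce on this point. The 30 per arm comes from section IV and the 4.9-point drug-placebo MADRS difference from section VII.A. All loss rates and outcome gaps below are assumptions.

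**1. Who is in the primary set**
- Randomised, leaves before any dose: out of the primary, completer and safety sets.
- Dosed, leaves before Week 1, no further rating: out of the primary set.
- Dosed, leaves before Week 1, attends the early-termination visit (which includes MADRS in V.C and XIV): in.
- Dosed, rated at least once, stops later: in, by LOCF.

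Only the first two groups are lost.

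**2. Whether an undosed interval exists**
- Reading A: an arm-specific taper (V.B) requires the arm to be known first, and VII.B randomises at the eligibility decision. V.C also lists an instruction for quetiapine-arm subjects under screening. The switch arm may then spend 2-4 weeks randomised and undosed.
- Reading B: XIV places randomisation at Week 0 and V.C dispenses drug at that visit, leaving little or no such interval.

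V.B does not say that the taper ends before the first levomilnacipran dose. The text does not settle the order.

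**3. Shift in the switch-arm mean**

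Let *f* be the fraction excluded and *g* the mean outcome of excluded minus retained patients. The full-arm mean is (1 − *f*) × retained + *f* × excluded, so the retained mean is too favourable by *f* × *g*.
- *f* = 0.10 (3 of 30), *g* = 6 points: 0.10 × 6 = 0.6 points, or 0.6/4.9 = 12% of the difference used in the power section.
- *f* = 0.17 (about 5 of 30), *g* = 8 points: 0.17 × 8 = 1.36, about 1.4 points, or 1.36/4.9 = 28%.

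**4. Loss in both arms**

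The bias in the comparison is *f*(switch) × *g*(switch) − *f*(quetiapine) × *g*(quetiapine). Three of 30 lost in each arm with the same 6-point gap gives 0.6 − 0.6 = 0. Greater loss on quetiapine reverses the sign.

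**5. Type I error, loss in the switch arm only**

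In SD units, bias *b* = (k/30) × gap and SE = √(1/(30 − k) + 1/30). The two-sided error is Φ(*b*/SE − 1.96) + Φ(−*b*/SE − 1.96).
- k = 3, SE = 0.265: gaps of 0.5 and 1.0 SD give *b* = 0.05 and 0.10, and error 0.054 and 0.066.
- k = 6, SE = 0.274: the same gaps give *b* = 0.10 and 0.20, and error 0.065 and 0.113.

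**6. Power**

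At d = 0.5, two-sided 0.05, normal approximation, power is 0.49 with 30 against 30, 0.47 with 27 against 30, and 0.45 with 24 against 30. The harm is mainly bias; little power is lost. (That 0.49 falls short of the plan's stated 0.80 is a separate matter.)

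**7. What a better model can restore**

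A patient with only a baseline score gives a likelihood model almost no information about the treatment effect. Missing-at-random imputation fills such a patient in from those retained. Either method reproduces nearly the same estimate as dropping the patient, so it cannot by itself remove the shift in step 3.

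**The case against.** The strongest reply accepts the definition and disputes what is built on it. Four inferences that a reader might draw go beyond the documents.

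- *The quetiapine arm has no period in which patients can be lost before drug.* Section V.B requires a 2-4 week washout of other psychotropics without limiting it to one arm, and V.C says that quetiapine-arm subjects undergo washout of other prohibited medications. Only the SSRI taper is specific to an arm.
- *The taper certainly falls between randomisation and first dose.* That is Reading A only; V.C and XIV support Reading B.
- *Everyone who leaves before Week 1 is excluded.* The early-termination visit includes a MADRS, so a dosed patient who attends it is kept.
- *The primary result is biased toward levomilnacipran.* Early unrated losses on quetiapine would push the other way, and no document gives a rate for either arm.

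It can also be said that the MADRS figures are products of assumptions, and that a missing-at-random analysis of all randomised patients would change little. Both are correct. Patients lost before Week 0 would also have only a screening MADRS.

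None of this restores the excluded patients. Even on Reading B, a dosed patient with no later rating is dropped, and the label remains wrong. The objections limit the claim about arm and direction, and they mean that the remedy needs more than a change of model.

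**Conclusion.** The point stands in two parts of different strength. It is certain from section VII.C that the primary set is a modified ITT set and that no planned efficacy analysis covers all randomised patients. It is conditional that exclusions fall more on the switch arm: this requires the taper to precede the first dose, on which the documents conflict. The comparison can then be biased, but direction and size are unknown. The illustrative 0.6 to 1.4 MADRS points assumes 10-17% lost from the switch arm, none from the quetiapine arm, and outcomes 6-8 points worse in those lost. If losses are balanced and similar, the bias is nil. The change should be made, because the cost is low and the protection concerns the primary comparison.

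**What to change.** 1. Define the primary set as all randomised patients, analysed as randomised. Use every available MADRS rating, including early-termination ratings and any ratings of undosed patients, in a likelihood-based repeated-measures model or multiple imputation instead of LOCF. Use the screening MADRS where no Week 0 score exists.
2. For patients with no post-baseline rating, add a sensitivity analysis assuming no improvement or worse outcomes, for example baseline carried forward or delta-adjusted imputation. Count them as non-responders and non-remitters.
3. Report by arm the numbers lost between randomisation and first dose, and between first dose and first rating.
4. Keep the current set, labelled modified ITT, as a sensitivity analysis.
5. Reconcile sections V.B, V.C, VII.B and XIV on the order of randomisation, taper, baseline MADRS and first dose.

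The cost is revised wording and a little more analysis work. The estimate for either strategy may be slightly less favourable. The planned visits need not change for items 1 to 4.

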The efficacy of extended-release (ER) levomilnacipran has been established for major depressive disorder (MDD) in doses ranging from 40 mg/day to 120 mg/day (Sambunaris et al, 2014; Asnis et al, 2013). Levomilnacipran is the most noradrenergically active of the SNRI class of antidepressant drugs. Levomilnacipran was found to have twofold greater potency for norepinephrine relative to serotonin reuptake inhibition, and 17 and 27 times higher selectivity for norepinephrine reuptake inhibition compared with venlafaxine and duloxetine, respectively (Auclair et al, 2013).

Cognitive dysfunction in MDD is common and associated with greater impairment in functioning and quality of life. Given the similarities in mechanisms of action, it is possible for levomilnacipran to have beneficial effects on neurocognition. Apathy is considered a disorder of motivation and can occur in neuropsychiatric syndromes as well as depression. It is associated with neurocognitive disturbances and functional impairment. It remains understudied in depression.

Augmentation by adjunctive atypical antipsychotics is recommended as one of the clinical strategies on par with antidepressant switch in the APA guidelines to treat MDD. Quetiapine (extended release) is an atypical antipsychotic approved as adjunct to antidepressants for treatment of MDD in doses between 150-300 mg/day and has been extensively used in clinical practice.

Needs assessment: There is a significant unmet clinical need in terms of patients with MDD who show inadequate response and remission with SSRI treatment. Scientific evidence that guides appropriate treatment strategies in terms of further steps of switching or augmentation of medications will improve clinical care in patients with MDD who do not show adequate response to SSRIs.

II. STUDY OBJECTIVE(S):

Primary:

1. To compare the efficacy and tolerability of switching to levomilnacipran ER (40-120 mg/d) versus augmentation with quetiapine 150-300 mg/day to the patients' existing treatment for patients with inadequate relief on generic SSRIs in patients with MDD.

Secondary:

1. To examine the response and remission rates following the switch from generic SSRI to levomilnacipran ER and augmentation with quetiapine.
2. To examine changes in neurocognitive and apathy measures after switching from SSRI to levomilnacipran and after augmentation with quetiapine in MDD

III. STUDY DESIGN and PLAN:

Methodology:

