Safety and tolerability will be assessed by spontaneously reported adverse events, Columbia Suicide Severity Rating Scale (CSSRS) Arizona Sexual Experience Scale (ASEX) scores, vital signs, weight and BMI measurements and clinical laboratory assessments and evaluating reasons for dropout from the trial.

Adverse event: any untoward medical occurrence associated with the use of a drug in humans, whether or not considered drug related.

Suspected adverse reaction: any adverse event for which there is a reasonable possibility that the drug caused the adverse event

Serious Adverse Event (SAE)

A serious adverse event is one that:

- Results in death
- Is an immediate threat to life?
- Requires inpatient hospitalization, or prolongation of existing hospitalization
- Results in persistent or significant disability/incapacity
- Is a congenital anomaly or birth defect.

Causality Assessment

For all AEs, the Investigator must provide an assessment of causal relationship to the IP.

Causal relationship must be assessed by answering the following question:

Is there a reasonable possibility the IP caused the event?

Yes: There is a possible or probable relationship (i.e., there is a reasonable or strong temporal relationship, and the events are unlikely to be attributable to other drugs, underlying diseases, or other factors). Challenge and/or rechallenge (if available) is positive.

No: The relationship is unlikely or nonexistent (i.e., there is no strong temporal relationship and/or the use of other drugs, underlying diseases, or other factors provide plausible explanations for the event), or the patient did not take the IP.

Reporting of Adverse Events:

All spontaneously reported and observed adverse events will be recorded in the source and CRF documents. The Principal Investigator will inform Actavis/Forest Global Drug Safety of all SAEs within 24 hours of first knowledge of any AE that meets one of the criteria for an SAE, on a SAE report form. If, during follow-up, any nonserious AE worsens and eventually meets the criteria for an SAE, that AE will be recorded as a new SAE.

The study centers will transmit the SAE report form to the SAE [contact]) within 24 hours of first awareness of the event at the study center. Supplemental information will be submitted as soon as available and may include laboratory results,

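### The safety population covers dosed patients only, so if the switch arm's SSRI taper falls between randomisation and first dose, withdrawals during it drop out of the tolerability comparison, in favour of switching

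*Combined protocol and SAP*

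**What the plan says.** Section II makes tolerability part of the primary objective, and frames it as a comparison of strategies: "To compare the efficacy and tolerability of switching to levomilnacipran ER (40-120 mg/d) versus augmentation with quetiapine 150-300 mg/day".

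Section V.B treats the existing antidepressant differently by arm. For the switch arm: "Subjects randomized to the Levomilnacipran switch arm will have their SSRI tapered over 2-4 weeks after they are determined to be eligible for the study". The reason it gives is the risk of a discontinuation syndrome. For the other arm: "Subjects randomized to the adjunctive quetiapine arm will have their pre-existing antidepressants continue unchanged at baseline". The taper period is followed by telephone: "Subjects will be monitored weekly by phone for side effects or symptom worsening during the taper". Section V.C adds that the calls cover depressive symptoms, suicidal risk and adverse events.

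Section VII (Statistical Evaluation), C, defines who is analysed for safety, "The safety population will comprise all patients receiving study drug with a post baseline safety assessment", and how: "Safety outcomes will be summarized by treatment group and study visit (observed cases) using descriptive statistics". No formal testing of safety data is planned.

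On timing, section V.C and the schedule of events (XIV) combine randomisation and baseline at Week 0, with first dispensing at the same visit, after a screening window that opens at Week -4. The schedule marks washout instructions at both Week -4 and Week 0.

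**The concern.** Stopping the SSRI is part of the switch strategy, and the protocol itself names its cost. If patients are assigned to an arm, tapered, and only then dosed, some of that cost arises before anyone in the switch arm has taken levomilnacipran. A safety population defined by dosing cannot contain a patient who leaves in that interval. The augmentation arm has no SSRI taper, so the loss is not balanced between arms.

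What is at stake is the tolerability half of the primary objective. Because safety is purely descriptive, the by-arm rates are themselves the evidence. If the denominator leaves out early failures of one strategy, that strategy looks better tolerated than it was.

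**Working it through.** The plan states no safety rate, so there is no figure to reproduce. The check has two parts.

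**1. Where the taper can fall**

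- *After randomisation, before first dose.* This is the literal reading of V.B: the taper applies to patients already assigned to switch, and an arm-specific taper needs a known arm. It also fits weekly phone calls, which would be largely redundant beside scheduled visits at Weeks 1, 2, 3 and 4. On this reading, a patient who withdraws during the taper is never dosed and is outside the safety population.
- *Before randomisation.* This fits the Week 0 label in V.C and XIV and the window from Week -4. Taper losses then belong to no arm and cannot bias the comparison.
- *Overlapping levomilnacipran dosing.* Taper events then fall at scheduled on-drug visits and are counted.

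Only the first reading produces the bias, and the documents do not settle which is meant.

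**2. What the first reading could do to the discontinuation rate**

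Inputs: 30 patients per arm (section IV.A); w = switch patients who withdraw during the taper (assumed, 1 to 6); p = discontinuation rate once on drug (assumed, 10% or 20%). Pre-dose withdrawals in the quetiapine arm are taken as zero.

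With q = w/30, the rate among all randomised to switch is q + (1 − q)p. The dosed-only rate is p. The understatement is the difference, q(1 − p).

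| w of 30 | q | All randomised, p = 10% | Understated by | All randomised, p = 20% | Understated by |
|---|---|---|---|---|---|
| 1 | 3.3% | 13.0% | 3.0 points | 22.7% | 2.7 points |
| 3 | 10.0% | 19.0% | 9.0 points | 28.0% | 8.0 points |
| 6 | 20.0% | 28.0% | 18.0 points | 36.0% | 16.0 points |

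Example: w = 3, p = 10% gives 0.10 + 0.90 × 0.10 = 0.19, against 0.10 in dosed patients.

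The ranking of the arms can also change. Suppose the dosed-only rates are 10% for switch and 20% for quetiapine. The all-randomised rates are equal when q + (1 − q) × 0.10 = 0.20, so q = 0.10/0.90 = 0.111, or 3.3 patients of 30. Three taper withdrawals shrink a 10-point advantage to 1 point (19% against 20%). Four reverse it: 4/30 = 0.133, and 0.133 + 0.867 × 0.10 = 0.22.

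**The case against.** The strongest objection is timing: the bias needs one of three readings, and the Week 0 entries in V.C and XIV speak against it. That stands, and it is why the conclusion is conditional. It does not remove the point, because the sentence in V.B is explicit that the patients tapered are those randomised to switch.

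Several other provisions limit how far the point reaches.

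- A reader might infer that every taper-phase adverse event is lost. The documents do not say so. All reported and observed events go into the CRF, adverse events are assessed at Week 0, and no treatment-emergent rule excludes pre-dose events. For patients later dosed the plan is silent; it does not exclude them. Any count that treats all taper events as uncounted is therefore unsupported.
- A reader might infer that the causality question, "Is there a reasonable possibility the IP caused the event", keeps discontinuation symptoms out of the tables. It does not. Adverse events are defined irrespective of causality, and the analysis plan does not restrict the summary to related events. The question classifies events and does not select them.
- A reader might infer that the quetiapine arm has no pre-dose phase at all. V.B and V.C allow for washout of other psychotropic drugs in that arm too, and some of its patients may change antidepressant. The sentence on phone monitoring follows the general washout rule, so it is not specific to the switch arm. The asymmetry is the SSRI taper alone.
- Reasons for dropout are listed as a tolerability measure without restriction to dosed patients, and clinically important findings in early terminators get a separate discussion. This is a partial safeguard. But no denominator or start point is set for dropouts, and a narrative is not a by-arm rate.

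Finally, no safety hypothesis is tested, so no p-value is affected. The descriptive comparison still is.

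**Conclusion.** The point holds in conditional form. If the SSRI taper falls after randomisation and before first dose, as V.B implies, switch patients who withdraw during it are excluded from the only safety population the plan defines. The handling of taper-phase events in patients later dosed is unspecified. The omission due to the SSRI taper affects one arm and favours switching, on a primary objective. V.B conflicts with V.C and XIV on the order of events, and the conflict decides whether the bias arises.

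The size cannot be estimated, because the documents give no adverse event, withdrawal or dropout rates. The 3 to 18 points (1 to 6 withdrawals of 30, on-drug discontinuation 10%) are an illustration. They assume no pre-dose withdrawals in the quetiapine arm; any that occurred would offset part of the difference between arms.

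**What to change.** 1. Reconcile sections V.B, V.C, VII (Statistical Evaluation) B and XIV on the order of randomisation, SSRI taper and first dose. The statistical point does not depend on which order is chosen, only on its being stated once and consistently.
2. Report adverse events and withdrawals by arm for all randomised patients, from randomisation to Week 9, including those recorded on the weekly phone calls. Show the pre-dose and on-drug periods separately and combined.
3. Keep the dosed safety population as a second table.

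If the reconciled text puts the taper before randomisation, the first table will contain no taper events, and the report should say so.

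The cost is a change of analysis wording and one extra table. The data are already to be collected, and no visit or clinical procedure is added. The downside is that the switch arm's tolerability figures may become less favourable.
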